9.1 TREATMENT/INTERVENTION PLAN

9.2 Study Assessments Visit Windows

Testing slots and procedure availability must be taken into consideration when scheduling study follow-up visits. Visits may be split across the window to permit for completion of all study-related assessments.

9.3 Evaluation Prior to Initiation of Intervention

Prior to the initiation of each intervention session participant resting vital signs will be assessed as per **Appendix H** to ensure the participant can safely proceed with the session. The planned session will not be initiated if the exercise physiologist observes any concerns that may compromise participant safety and/or the integrity of the planned session.

9.4 Study Interventions

The study interventions are supervised linear aerobic training (Arm A), supervised nonlinear aerobic training (Arm B), or progressive stretching (attention control) (Arm C). All sessions will be performed in a supervised setting by a Ex-Onc exercise physiologist. Sessions will take place at the Sidney Kimmel Center for Prostate and Urologic Cancers or Sillerman Center for Rehabilitation.

All aerobic training sessions will be prescribed by an exercise physiologist under the direction of the Program Director. All exercise physiologists are trained in either Basic or Advanced Cardiovascular Life Support (BLS/ACLS).

Participants will be instructed to adhere to fasting guidelines for food, caffeine, tobacco, alcohol and exercise as outlined in Appendix H.

All sessions, regardless of randomization arm, will include a warm-up. The aerobic arms, A and B, will also include a cool-down. Heart rate, oxygen saturation and blood pressure will be

assessed prior to and following each intervention session. All adjustments to the intervention sessions will be implemented according to the standard care procedures of the exercise physiologists and will be source documented.

9.3.1 Arm A — Linear Aerobic Training

The ultimate goal is for participants to complete approximately 130–180 minutes/week of aerobic training, at 60% to 75% of the individually determined exercise capacity (VO_{2peak}), for 16 weeks. VO_{2peak} will be determined by the second CPET performed at baseline. The weekly exercise will be achieved via either 3 to 4 individual aerobic training sessions (**see Appendix H**). All sessions are required to be supervised. Intensity and duration of aerobic training is prescribed and is implemented in accordance with standard exercise training principles. This approach will be applied to guide each participant's prescription, with dose and scheduling modifications made by exercise physiologists, as required.

9.3.2 Arm B — Nonlinear Aerobic Training

The ultimate goal is for participants to complete approximately 130–180 minutes/week of aerobic training at 55% to 100% of the individually determined exercise capacity (VO_{2peak}), for 16 weeks. VO_{2peak} will be determined by the second CPET performed at Baseline, as well as the CPET performed at midpoint. The weekly exercise will be achieved via 3 to 4 individual aerobic training sessions (**see Appendix H**). All sessions are required to be supervised. Intensity and duration of aerobic training is prescribed and is implemented in accordance with standard exercise training principles (e.g., in a progressive manner with planned recovery between high-intensity sessions). This approach will be applied to guide each participant's prescription, with dose and scheduling modifications made by exercise physiologists, as required.

9.3.3 Arm C — Progressive Stretching Group (Attention control)

The ultimate goal for the progressive stretching program is 3 to 4 individual stretching sessions (**see Appendix H**). All sessions are required to be supervised. Duration of the stretching sessions is prescribed and implemented in accordance with standard stretching and flexibility training principles. This approach will be applied to guide each participant's prescribed stretching plan, with dose and scheduling modifications made by exercise physiologists, as required.

9.4 Early Termination of Intervention Sessions (Aerobic and Stretching)

All intervention sessions will be immediately terminated if, at any time during a session, any adverse clinical signs and symptoms that will not allow the intervention to proceed safely are observed by the exercise physiologist. Determination of whether it is safe for the intervention to resume in the same session — for example, if the signs and symptoms are sufficiently subsided by a rest period — will be determined by the exercise physiologist.

In the event of a session termination, the appropriate medical follow-up and clearance will be performed as per post-training clearance criteria specified in the —Training Session Criteriall section of Appendix H. All signs and symptoms that result in session termination will be

source documented and reported as an adverse event to the study intervention. Future planned training sessions will continue at the discretion of the PI.

9.5 Intervention Session Dose Modification (Aerobic and Stretching)

Vital signs will be monitored during intervention sessions to ensure participant safety. Vital sign changes that are outside the expected range of the intervention will be monitored by the exercise physiologist. The exercise physiologist will use clinical discretion to determine if a modification to the prescription or termination of the session is required.

All modifications will be source documented and recorded in the study database, including the modification reason, how the session was modified, and clearance obtained, as appropriate.

Participants requiring consistent modification of the planned prescription will be reviewed by the study PI and exercise physiologists to determine appropriate action (e.g., early study withdrawal, physiological re-evaluation).

Final determination of the intensity and duration of the session against the planned session goals will be conducted by the supervising exercise physiologist following the session and will be source documented.

9.6 Study Intervention Continuation/Interruption

If a session is missed or interrupted for an adverse event (AE), the participant will be treated for the AE as per the discretion of the attending oncologist and/or PI, as appropriate. The participant will resume the intervention only after clearance from the PI.

Participants with treatment interruptions lasting longer than 4 consecutive weeks will be discontinued from the trial. In addition, any participant who misses a cumulative total of 8 weeks of the study intervention will be discontinued from trial participation. When appropriate, study follow-up assessments will still be performed.

When intervention sessions are resumed, the dosing will be progressively increased until the planned prescription can be safely resumed, according to the Ex-Onc Exercise Physiology standards of care and/or at the discretion of the Program Director.

Participants will be allowed to make up missed sessions within the 16-week study window. Participants are not allowed to *a priori* bank aerobic training sessions.

Participants experiencing disease recurrence will be removed from study.

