13.0 CRITERIA FOR REMOVAL FROM STUDY

The primary reasons for permanent intervention discontinuation are listed in **Table 3**.

Table 3. Primary Reasons for Permanent Intervention Discontinuation

Reason	Description
Self-withdrawal (withdrawal of consent)	Participants may permanently discontinue study intervention and withdraw from the study at any time for any reason. Following study intervention discontinuation, participants should have protocol-required follow-up assessments unless the participant specifically declines further follow-up.
Adverse event or intercurrent illness	Any intolerable adverse event (associated or not associated with the study intervention) that cannot be ameliorated by the use of adequate medical intervention or that, in the opinion of the principal investigator, would lead to undue risk if study intervention were continued.
Gross non-compliance with protocol (violation)	The investigator may request permanent discontinuation of the study intervention in the event of lack of cooperation or complete noncompliance.
Disease progression	Study intervention will be discontinued upon histologically-confirmed diagnosis of invasive breast cancer or DCIS found during standard of care screening.
Lost-to-follow-up	Reasonable effort should be made to contact any participant lost to follow-up during the course of the study in order to complete study-related assessments and record outstanding data.
Death	N/A

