14.3 Primary and Secondary End Point Analyses

14.3.1 Primary End Point Analysis: The primary objective will be to compare the effects of supervised linear aerobic training (Arm A) versus supervised nonlinear aerobic training (Arm B), relative to progressive stretching (attention-control group) (Arm C), on VO_{2peak} in women with operable breast cancer following the completion of primary adjuvant therapy.

An intent-to-treat statistical analysis will be conducted. Baseline characteristics will be compared using the Fisher exact test for categorical variables or a Wilcoxon rank sum test for continuous variables. The primary end point comparison will be analyzed using a multiple regression model to test for differences among and between the study arms in VO_{2peak} from baseline to the follow-up assessment (Week 17). The regression model will include the stratification factors [i.e., treatment with chemotherapy (yes vs. no) and current treatment with endocrine therapy (yes vs. no)].

In the absence of evidence to the contrary, multiple imputation strategies for missing Week 17 VO_{2peak} data will be performed assuming data were missing at random using logistic regression. Results will be aggregated over 20 imputed sets using the variance formula by Rubin. In addition, a per-protocol analysis will be performed using a multiple regression model to test for differences among and between the study arms in VO_{2peak} from baseline to the follow-up assessment (Week 17) on the basis of exercise adherence to the supervised aerobic training sessions (<80% versus ≥80%). In the event that groups are unbalanced on medical or demographic characteristics at baseline, we will also perform a sensitivity analysis that includes these factors in the model.

14.3.2 Secondary End Point Analyses: As for the primary end point, the intention-to-treat principle will be employed for analysis of all secondary end points. Multiple regression models will be used to test for differences among and between the study arms in secondary end points from baseline to the follow-up assessment (Week 17). The regression model will include the baseline value of the end point, as well as any other baseline characteristics that are not balanced between groups. All secondary end points are continuous.

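### Section 9.6 takes women with long interruptions out of the trial, not only the intervention, and leaves their Week 17 test to an undefined judgement, at odds with Table 3 and the intent-to-treat plan

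*Combined protocol and SAP*

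**What the plan says.** Section 9.6 sets two exposure thresholds. For the first, "Participants with treatment interruptions lasting longer than 4 consecutive weeks will be discontinued from the trial". For the second, "any participant who misses a cumulative total of 8 weeks of the study intervention will be discontinued from trial participation". The only provision for outcome data after either is "When appropriate, study follow-up assessments will still be performed", with no criterion and no named decision-maker. The section also states that "Participants experiencing disease recurrence will be removed from study" and that "Participants will be allowed to make up missed sessions within the 16-week study window".

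Table 3 in Section 13.0 reads differently. Its self-withdrawal row says: "Following study intervention discontinuation, participants should have protocol-required follow-up assessments unless the participant specifically declines further follow-up". Its disease-progression row speaks of discontinuing the intervention. Its lost-to-follow-up row asks for reasonable effort to complete assessments. Interruption length is not among the listed reasons.

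On analysis, Section 14.3.1 says "An intent-to-treat statistical analysis will be conducted". Missing Week 17 VO2peak is to be multiply imputed (20 sets) under missing at random, unless there is evidence to the contrary. No imputation predictors are listed. Section 14.2 invokes intention-to-treat and counts all 174 women as having evaluable follow-up, with no allowance for loss.

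**The concern.** An intent-to-treat comparison needs the outcome from every randomized woman, whatever she received. Section 9.6 merges stopping the intervention with leaving the trial. It then makes collection of the primary outcome optional for a group defined by low exposure. The staff who would judge whether testing is appropriate know the arm (Section 7.1, Blinding).

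A woman who stopped training early may well have gained less than others in her arm. If she is not tested, and the imputation model does not know that she stopped, her imputed value will tend to resemble those of women who trained and were tested. Arm B has the largest planned gain (+4.0, against +1.5 in Arm A and 0.0 in Arm C). An error of this kind would therefore tend to favour Arm B in both primary comparisons, B versus A and B versus C. Outcomes that were never collected cannot be recovered at the analysis stage.

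**Working it through.** **Inputs.** Section 14.2: planned changes A +1.5, B +4.0, C 0.0 mL/kg/min; SD of change 4.0; 58 per arm; two-sided alpha 0.025. Section 9.7: 64 planned sessions, 4 per week for 16 weeks. Section 1.0: 115 women already randomized (38, 39, 38), with 20, 19 and 20 to come at MSK. Loss at the first site, all causes and all arms: 6/115 = 5.2% (Section 1.0) or 9/115 = 7.8% (Section 16.3, Current Status). Mean adherence in Arms A and B: 77% (Section 16.3).

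**1. The plan's power figure.** The standard error of a pairwise difference is 4.0 × √(2/58) = 0.743. The noncentrality is 2.5/0.743 = 3.37 on 114 degrees of freedom, which gives 86.2% power for A versus B. The stated 86% is reproduced. It rests on nobody lacking a Week 17 value. With complete cases only, power is 84.1% at 5.2% loss and 82.9% at 7.8% loss. The loss of power is small, so the question is mainly one of bias.

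**2. Does the rule select on exposure?** Before make-up sessions:
- More than 4 weeks missed: attendance of at most (64 − 16)/64 = 75%.
- 8 weeks missed: attendance of at most (64 − 32)/64 = 50%.

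Both lie below the 80% adherence cut in Section 14.3.1, so the rule does select on low exposure. But 75% is close to the 77% mean. A woman with one interruption of just over 4 weeks need not be among the least trained.

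**3. Does Table 3 override Section 9.6?** Not clearly. The follow-up sentence sits only in the self-withdrawal row, and Section 9.6 is the only text written for women who reach an interruption threshold. On recurrence, one passage removes the woman from study and the other discontinues the intervention.

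**4. Would the imputation correct it?** That cannot be told from the plan. Neither attendance nor discontinuation is named as a predictor, and no missing-not-at-random sensitivity analysis is planned. Only Arm B has a midpoint CPET (Section 10.1), so Arms A and C have no on-treatment VO2peak to inform imputation.

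**5. Illustrative size.** Assumptions, none taken from the documents: 5% to 10% of affected women in each training arm go untested, their true change is 0, and they are imputed at the planned arm mean. Arm C adds no bias because its planned change is 0.

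Bias in an arm = share untested × (imputed change − true change).

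| | 5% untested | 10% untested |
|---|---|---|
| B − C, whole trial | 0.05 × 4.0 = 0.20 | 0.10 × 4.0 = 0.40 |
| B − A, whole trial | 0.05 × (4.0 − 1.5) = 0.125 | 0.10 × 2.5 = 0.25 |
| B − C, MSK only | 19/58 × 0.20 = 0.066 | 19/58 × 0.40 = 0.131 |
| B − A, MSK only | 0.066 − (20/58 × 0.05 × 1.5) = 0.040 | 0.131 − (20/58 × 0.10 × 1.5) = 0.079 |

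The MSK-only rows correspond to about 1 to 2 women per training arm (5% to 10% of 19 or 20). The B − A values are 1.6% to 3.2% of the planned 2.5, and well inside one standard error (0.743).

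**The case against.** The strongest reply is that nothing in the text requires an outcome to be lost. Section 9.6 says assessments will still be done, and its qualifier can be read as ordinary caution about consent and safety before a maximal exercise test. Table 3 asks for follow-up unless the woman declines. Women without a Week 17 value stay in the analysis through imputation. Attendance is calculated for every participant and could be used as a predictor, and the missing-at-random assumption is itself conditional.

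Much of this stands. A reader might infer that the rule strips the least-trained women of the primary outcome or drops them from the analysis. The documents do not support that: testing is permitted, imputation keeps the women in, sessions can be made up, interruptions may come late, and the rule applies to the stretching arm too. A reader might also take the whole-trial figures, 5% to 10% of the planned B minus A difference, as the expected bias. They are not. The upper share exceeds both reported all-cause losses, and the lower share would attribute nearly all of the smaller one to this rule. Section 16.2 (Role of DUMC) says that first-site participants completed study procedures, so new wording can reach only the 59 women enrolled at MSK. Zero true change is also a pessimistic value.

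What does not fall away is the conflict itself. A qualifier with no criterion, applied by unblinded staff to women selected for low exposure, is weaker than the follow-up that Sections 13.0 and 14 presuppose. Imputation predictors that could be used are not the same as predictors that are specified.

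**Conclusion.** The point holds as an inconsistency with a plausible direction of bias, not as a demonstrated bias. Section 9.6 ties leaving the trial to low exposure and makes Week 17 testing discretionary. Table 3, the intent-to-treat analysis and the count of 174 evaluable women all assume otherwise. Low-exposure women may go untested, and the imputation as written may give them values that are too favourable, which would tend to help Arm B.

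Under the stated assumptions, with only MSK participants affected, B minus C would be overstated by about 0.07 to 0.13 mL/kg/min and B minus A by about 0.04 to 0.08. The corresponding figures are 0.20 to 0.40 and 0.13 to 0.25 if the whole trial were affected. The real size is unknown, because the documents do not say how many women met the thresholds or went untested. The effect is probably modest, but it is avoidable and the remedy is cheap.

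**What to change.** 1. In Section 9.6, reword both threshold sentences so that the woman is discontinued from the intervention, not from the trial or from trial participation. The 4-week and 8-week thresholds are not touched.
2. Replace the qualifier that opens "When appropriate, study follow-up assessments will still be performed" with a statement that Week 17 assessments, at minimum the CPET, are sought for every randomized participant unless she declines or testing is judged unsafe.
3. Reconcile "Participants experiencing disease recurrence will be removed from study" with the disease-progression row of Table 3, so that it is clear what ends and what continues.
4. In Section 14.3.1, name attendance or discontinuation status as a predictor in the imputation model for any Week 17 values still missing. Unlike the wording changes, this can also serve missing values from the first site where attendance was recorded.

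The cost is a short amendment and some extra effort to bring discontinued women back for a visit that Table 2 already schedules for all arms.

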9.7 Study Intervention Attendance and Compliance

Attendance is calculated as the number of intervention sessions attended divided by the total number of planned sessions (i.e., 4 times/week x 16 weeks = 64). *Compliance* is calculated as the number of intervention sessions attended, as well as whether the training session dose was successfully completed (i.e., participant completed the intervention session at the

planned duration and intensity) divided by the total number of planned sessions. *Non-compliance* is defined as any intervention session requiring dose modification of either the planned intervention duration and/or intensity.

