10.1 Cardiopulmonary Exercise Testing (CPET)

The midpoint CPET will take the place of one aerobic training session during Week 8 for participants in Arm B. This test is repeated at this time point to re-assess VO_{2peak} under the expectation that VO_{2peak} is likely to have changed in the first 8 weeks of the aerobic training program. Thus, information from midpoint testing is used to re-prescribe the aerobic training prescription to ensure continual physiological adaptations across the entire study period.

This test will not be repeated in the linear aerobic training prescription group (Arm A) or the progressive stretching group (Arm C) at Week 8.

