16.3 Current Status

As of September 2013, the trial status is as follows: The grant was released on 10/09/2009 and the protocol received Institutional Review Board (IRB) approval from DUMC on 03/25/2010. As of September 2013, a total of 115 patients (of a planned 174 participants; 66%) had been recruited and randomized. Of these, 106 patients (92%) successfully completed study procedures, with 9 patients lost-to-follow-up (8%). The mean adherence rate was 77% across Arms A and B, with minimal adverse events, suggesting that all intervention sessions were well-tolerated.

Additional details are available. Overall, we were pleased with the study progress at the time of trial suspension and patient self-reports of the benefits of the trial.

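### Attendance is scored out of 64 sessions for everyone although 3 to 4 a week are allowed, so a woman planned at 3 a week cannot reach the 80% per-protocol cut

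*Combined protocol and SAP*

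**What the plan says.** Section 9.7 gives attendance as the "number of intervention sessions attended divided by the total number of planned sessions (i.e., 4 times/week x 16 weeks = 64". The 64 is offered as the meaning of the planned total, not as an example, and no individual denominator is mentioned. Compliance counts only sessions both attended and completed at the "planned duration and intensity) divided by the total number of planned sessions", so it has the same denominator.

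The intervention sections are looser on frequency. For Arm A, Section 9.3.1 says: "The weekly exercise will be achieved via either 3 to 4 individual aerobic training sessions". For Arm B, Section 9.3.2 says: "The weekly exercise will be achieved via 3 to 4 individual aerobic training sessions". For Arm C, Section 9.3.3 says: "The ultimate goal for the progressive stretching program is 3 to 4 individual stretching sessions"; it gives no period, though a week is presumably meant. All three refer to Appendix H for detail.

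Section 14.3 (14.3.1 for the primary end point, 14.3.2 for the secondary ones) adds per-protocol regressions "on the basis of exercise adherence to the supervised aerobic training sessions (<80% versus ≥80". Adherence is not defined there or elsewhere.

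Two further passages bear on the count. Section 10.1 says: "The midpoint CPET will take the place of one aerobic training session during Week 8 for participants in Arm B"; Section 9.7 does not say whether that test counts as an attended session. Section 16.3 says of the DUMC participants: "The mean adherence rate was 77% across Arms A and B", without giving the denominator.

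**The concern.** A per-protocol split should separate women who followed what was planned for them from those who did not. If the denominator is 64 for everyone while some plans contain fewer sessions, a woman can follow her plan completely and still be put with the non-adherent. The split would then mix two things: how many sessions she attended, and how many she was scheduled for.

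The affected outputs are the per-protocol analyses of the primary and secondary end points and any reported attendance or compliance rate. The undefined term adds to the problem: the denominator and the choice between attendance and compliance would be settled at analysis, possibly with the results in view.

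**Working it through.** **Inputs.** Programme length: 16 weeks (Section 7.2). Sessions per week: 3 to 4 (Sections 9.3.1 and 9.3.2). Denominator: 64 (Section 9.7). Cut: 80% (Section 14.3).

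**The plan's own figure.** 4 × 16 = 64. It reproduces.

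**Range allowed by the intervention sections.** 3 × 16 = 48 and 4 × 16 = 64.

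**Sessions needed to reach the cut.** 0.80 × 64 = 51.2, so 52 sessions, an average of 52/16 = 3.25 a week.

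**Best possible score at 3 a week throughout.** 48/64 = 75.0%, below the cut. Section 9.6 allows missed sessions to be made up within the 16 weeks and bars banking sessions in advance. Make-ups therefore restore missed sessions and do not lift her above 48.

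**Mixed schedules.** If w of the 16 weeks are planned at 4 sessions and the rest at 3, full attendance gives 48 + w sessions:

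| w | sessions | score out of 64 | class |
|---|---|---|---|
| 0 | 48 | 75.0% | below 80% |
| 3 | 51 | 79.7% | below 80% |
| 4 | 52 | 81.3% | 80% or more |
| 8 | 56 | 87.5% | 80% or more |
| 16 | 64 | 100% | 80% or more |

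So a fully attending woman reaches the cut only if w is at least 4.

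**Does it matter which measure *adherence* means?** No. Compliance has the same denominator, and its numerator is a subset of the sessions attended, so it cannot exceed attendance. The 75% ceiling holds under both.

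**Arm B's Week 8 CPET.** If the test is not counted as a session, the maxima are 63/64 = 98.4% at 4 a week and 47/64 = 73.4% at 3 a week. The difference is 1/64 = 1.6 percentage points.

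**The DUMC 77%.** If the denominator was 64 (assumption), 0.77 × 64 = 49.3 sessions, slightly more than a complete 3-a-week programme (49.3/48 = 1.03). If it was 48 (assumption), 0.77 × 48 = 37.0 sessions. The documents do not say which applies.

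**With each woman's own planned total as denominator.** A full 3-a-week programme scores 48/48 = 100%. The cut then needs 39 of 48 sessions (0.80 × 48 = 38.4) or 52 of 64.

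**The case against.** The best counter-reading is that 4 a week is the plan for everyone, as the formula in Section 9.7 suggests, and that 3 to 4 only describes how the weekly minutes may be achieved. Then 64 is the right denominator and nobody is misclassified. The text reviewed cannot exclude this: no section shows that any woman is planned at 3 a week for all 16 weeks, and Appendix H is not available. What survives is that the sections do not agree as written, and that 3 a week lies within the stated plan.

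A second objection is that a fixed 64 measures delivered dose and so has a use. That is fair, but delivered dose is a different quantity from following one's plan. A related warning also stands. Sections 9.3.1, 9.3.2, 9.5 and 9.6 let staff modify dose and scheduling after randomisation. If the denominator were whatever was finally prescribed, it would shrink whenever sessions were cut back, and a woman on a much reduced plan could score 100%. The denominator therefore has to be fixed at the start.

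A reader might also draw stronger conclusions that the documents do not support:

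- *That the split merely separates women scheduled for 4 from those scheduled for 3.* A woman planned at 4 a week must still attend 52 sessions, so attendance still drives the split.
- *That the DUMC 77% is understated.* That depends on a denominator that is not given.
- *That selection differs between Arms A and B.* Nothing shows a different frequency mix by arm, and the CPET effect is at most 1.6 points and depends on an unstated counting rule.
- *That the per-protocol comparison loses a particular amount of power.* The documents do not say how many women would clear the cut, or whether those below it are excluded.

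**Conclusion.** The concern holds in a limited form. As written, Section 9.7 caps a woman planned at 3 sessions a week throughout at 75%, five points below the cut in Section 14.3, however well she attends. A fully attending woman needs at least 4 weeks planned at 4 sessions to be classed as adherent.

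This rests on two assumptions: that *adherence* in Section 14.3 means one of the two measures in Section 9.7, which are the only ones defined, and that some women are planned below 3.25 sessions a week on average. The first is a reasonable inference. The second cannot be checked, so the number of women affected is unknown.

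It would be wrong to infer that the main result is at risk. The intention-to-treat analysis and the sample size do not use attendance. Only the supportive per-protocol analyses and adherence reporting are affected. The correction is worth making before analysis because it is cheap and removes a later choice of denominator.

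**What to change.** 1. Reconcile Section 9.7 with Sections 9.3.1 to 9.3.3 on the planned number of sessions. This concerns the measure only; the prescription need not change, and no view is taken here on which frequency is right.
2. In Sections 14.3.1 and 14.3.2, define adherence as sessions attended divided by the number of sessions in that woman's plan as initially set after randomisation. State that later modifications and missed sessions do not reduce the denominator. Attendance is preferable to compliance, because Section 9.7 treats any session with a modified dose as non-compliant even though modification is permitted. If every initial plan proves to contain 64 sessions, this definition returns 64 for everyone and nothing is lost.
3. State that a completed Week 8 CPET in Arm B counts as an attended session.
4. Report the denominator behind the DUMC 77%, and recompute the figure on the new basis where the records allow.

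**Cost.** A few sentences in Sections 9.7, 14.3.1 and 14.3.2, and a little extra derivation work. No additional patients or assessments are needed. The main burden is that initial planned session counts may have to be recovered for the 115 DUMC participants: Section 9.5 requires modifications to be recorded, but the protocol does not show that planned counts were kept at DUMC.

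### The fixed 64-session denominator scores full attendance on an allowed 3-per-week schedule at 75%, below the 80% per-protocol cut-off

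*Combined protocol and SAP*

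**What the plan says.** Section 9.7 (Study Intervention Attendance and Compliance) defines two measures. Attendance is the number of sessions attended "divided by the total number of planned sessions (i.e., 4 times/week x 16 weeks = 64"). Compliance also requires that each counted session was completed at its "planned duration and intensity) divided by the total number of planned sessions", so it has the same denominator.

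The arm descriptions give a range. For Arm A: "The weekly exercise will be achieved via either 3 to 4 individual aerobic training sessions". For Arm B: "The weekly exercise will be achieved via 3 to 4 individual aerobic training sessions". For Arm C: "The ultimate goal for the progressive stretching program is 3 to 4 individual stretching sessions", with no time unit in that sentence. All three refer to Appendix H for detail; it is not part of the text available for this review.

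Sections 14.3.1 and 14.3.2 add a per-protocol regression for the primary and every secondary end point, "on the basis of exercise adherence to the supervised aerobic training sessions (<80% versus ≥80"%). The term adherence is not defined there or elsewhere. Under Section 10.1, "The midpoint CPET will take the place of one aerobic training session during Week 8 for participants in Arm B". Section 16.3 reports experience before the trial was suspended: "The mean adherence rate was 77% across Arms A and B".

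**The concern.** A schedule that the protocol allows cannot reach the protocol's own adherence threshold. If some participants are prescribed 3 sessions a week and others 4, the split at 80% reflects prescribed frequency as well as behaviour, and full attenders on the lower frequency are classed with those who missed sessions. Reported attendance and compliance rates carry the same distortion.

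Two gaps in Section 14.3 add to this. Because adherence is undefined, the analyst must choose between attendance and compliance in an open-label trial. And the cut is worded for aerobic training, while the per-protocol model compares all three arms. Arm C has no aerobic sessions (Table 2, footnote 6, limits them to Arms A and B), so it is unclear whether Arm C is left unselected, excluded, or judged on stretching attendance. That matters for Arm B versus Arm C, one of the two primary pairwise comparisons in Section 14.2.

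**Working it through.** Inputs: 4 sessions per week, 16 weeks and a total of 64 (Section 9.7); 3 to 4 sessions (Sections 9.3.1 to 9.3.3); 80% cut (Sections 14.3.1 and 14.3.2); one Arm B session replaced at Week 8 (Section 10.1); 77% mean adherence (Section 16.3).

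1. The plan's own figure: 4 × 16 = 64. It reproduces.
2. Sessions needed to pass: 0.80 × 64 = 51.2, so 52. Check: 51/64 = 79.7% fails and 52/64 = 81.3% passes. The average needed is 52/16 = 3.25 per week.
3. Full attendance at 3 per week: 3 × 16 = 48, and 48/64 = 75.0%. This fails.
4. Compliance counts only attended sessions completed as planned, so it cannot exceed attendance. At 3 per week it is at most 75.0% and also fails.
5. Mixed schedules: with k weeks of 4 sessions and the rest at 3, the total is 48 + k. Passing needs 48 + k ≥ 52, so k ≥ 4. A participant with full attendance fails if she is prescribed 3 per week in 13 or more of the 16 weeks.
6. Make-up sessions (Section 9.6) replace missed sessions. A full attender has none to make up.
7. Arm B, if the Week 8 test is not counted as a session: the ceiling is 63/64 = 98.4% at 4 per week and 47/64 = 73.4% at 3 per week. One session is worth 1/64 = 1.6 percentage points, and neither ceiling crosses 80%.
8. With the participant's own prescription as denominator, full attendance at 3 per week is 48/48 = 100%. The 80% cut is then 0.80 × 48 = 38.4, so 39 sessions (39/48 = 81.3%).
9. The 77% mean, if it was computed on 64, is 0.77 × 64 = 49.3 sessions, or 3.08 per week. That is compatible with near-full attendance at 3 per week and with 77% attendance at 4 per week. The figure cannot separate the two, and its denominator is not stated.

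**The case against.** The strongest reply is that nobody is shown to be affected. The arm descriptions speak of an ultimate goal, allow scheduling changes, and leave the detail to Appendix H. The range could describe a build-up to 4 per week, or a reduction from a planned 4. In the latter case 64 is the intended dose, and a participant on 3 did receive less. This stands as far as the number affected goes: it is unknown. It does not remove the conflict, because the body of the protocol presents 3 sessions as an acceptable way to deliver the weekly training and gives no denominator other than 64.

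It can also be said that Section 14.3 never ties adherence to Section 9.7. That is right: the link is an inference. It is a sound one, since Section 9.7 offers only two measures and both give at most 75% at 3 per week.

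On Arm C, Section 9.7 speaks of intervention sessions, which would include stretching, and Section 10.3 uses the aerobic-session phrase for all arms. So the wording is ambiguous; it does not establish that controls would go unselected.

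A reader might infer two stronger points. One is that, with a mean of 77%, most of Arms A and B would fail the cut and per-protocol power would collapse. The documents give no spread for adherence and no denominator for the 77%. They also do not say whether participants below 80% are dropped or analysed as a stratum. Any such loss would come from placing an 80% cut on a 77% mean, whatever the denominator. The other is that the Week 8 test biases Arm A against Arm B. The effect is 1.6 points, moves neither ceiling across 80%, and arises only if the test counts as a missed session, which Section 10.1 does not say.

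**Conclusion.** The point holds and should be fixed. As written, full attendance at 3 sessions per week scores 75% and is classed below 80%; at least four 4-session weeks are needed to pass. This rests on two assumptions: that adherence in Section 14.3 means attendance or compliance as defined in Section 9.7, and that some participants are prescribed 3 per week for nearly the whole intervention. The first is a sound inference. The second cannot be checked from the documents, so no misclassified share can be given.

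The reach is limited to the per-protocol analyses of the primary and secondary end points and the attendance and compliance reports. The intention-to-treat primary analysis and the sample size do not depend on this denominator, so the matter falls short of a fault that must be cured before the trial can be interpreted.

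**What to change.** Reconcile the frequency in Sections 9.3.1 to 9.3.3 with the 4 per week in Section 9.7. This review takes no view on which is right.

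In Section 14.3:
- Define adherence as one named measure from Section 9.7.
- Set its denominator to the number of sessions in the participant's initial prescription, not reduced by later modifications or missed sessions. Sessions actually scheduled would be a poor choice: staff are unblinded (Section 7.1, Blinding) and may alter schedules, so the denominator could shrink for participants who struggle.
- State that the Arm B Week 8 test is not counted as a missed session.
- Apply the same 80% rule in all three arms, using stretching sessions for Arm C.
- Include baseline VO2peak and the stratification factors in the per-protocol model. This reduces the selection of better adherers that any per-protocol comparison carries, but does not remove it.

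The wording change is small. The real cost is that 115 of the 174 participants were randomized at the Duke site, and nothing in the documents shows that their prescribed session counts can be recovered. These must be confirmed. Where they cannot be recovered, report the result on the 64 denominator as a sensitivity analysis.
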